*****See Next Page for Figure*****

A. Influence of Aging on IGF1 mRNA levels

B. TIMP1 Response to Exercise

[figure not shown]

[figure not shown]
Figure 4: Influence of aging and exercise on muscle mRNAs. A. IGF1 mRNA is lower in muscle of old than young adults before and after exercise ($P<0.05$). Box plots denote the medians (line), 25th and 75th percentiles (boxes), 10th and 90th percentiles (whiskers), and outliers (dots). B. TIMP1 mRNA increases in muscle of young ($P<0.05$) but not old adults after exercise. Median (triangle) and individual subject responses (line) are shown.

Finding 4: Muscle expression of genes associated with inflammation, growth, and remodeling is strongly correlated in older adults with muscle size and strength gained from resistance training [3].

Study: Older (61-78 yrs) men (N=3) and women (N=5) completed 12-weeks of high-intensity progressive resistance training of the thigh muscles. Biopsies were collected prior to training and analyzed by real-time PCR and immunohistochemistry. Muscle size change range from -1% to +18% while strength increase ranged from +8% to +65%. Strength gain correlated ($R > 0.7$, $P < 0.05$) with expression of mRNAs encoding cytokines (IL1 β , IL10, IL1RA), growth (CNTF, GDF8, IGF1, IGFBP5) and remodeling factors (MMP2, TIMP1). The result is shown for IGF1 in Figure 5A. Strength gain also correlated with the number of CD163+ macrophages in muscle with the exception of one outlier (Figure 5B). Similar results were found for muscle size.

Conclusions: Macrophages and mRNAs associated with inflammation, growth, and remodeling appear to be involved with adaptation to exercise in older adults. However, these variables could be covariates affected by an unknown determinant of muscle adaptation. The proposed study will allow investigation into whether macrophage function or immune function in general influences adaptation to resistance training in older adults.

A. IGF1 versus Strength Gain

B. CD163 Macrophage Number versus Strength Gain

[figure not shown]
[figure not shown]

Figure 5. Relationship between baseline molecular and cellular measures for muscle of older adults and percent strength gain for knee extension after 12-weeks of training. A. Pearson correlation for IGF1 mRNA and strength gain (triangles = males, circles = females). B. Relationship between number of muscle macrophages and strength gain.

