STATISTICAL PLAN: The sample size (N=50) provides greater than 80% power for Aims 1-3 to detect mean differences between groups of 0.8 to 0.85 standard deviation (SD) units at a 5% level of significance. Power calculations were based on using a one-sided t-test to compare independent groups using data from our work and others [2;23;65] though non-parametric tests or transformations will be used as necessary for data containing outliers. There is no formal plan to adjust for multiple comparisons. However, multiple correlation analysis will be used to determine the correlation between endpoints and any possible inflation in the overall Type I error rate. This analysis will allow testing of the overall hypothesis that measures of immune function (Aim 1) will be positively correlated with adaptations to exercise (Aim 2) and retention of muscle strength, mass, and function after exercise training is halted (Aim 3). The hypotheses are stated for each aim and the time points for comparison are listed in Table 6.

Aim 1 Power: Aim 1 will determine if the supplement consumption for 2-weeks improves baseline measures of immune function or the immune responses to vaccination or acute exercise. The representative measures chosen to calculate power are change in muscle macrophage content after exercise (Finding 2) and change in CRP levels post-supplementation (Pilot Study Finding 1). Przybyla et al detected a 29% increase in CD163+ macrophages in young subjects after exercise but no change in older subjects [2]. Power for this aim is calculated to detect at least a 29% greater increase in macrophages in the supplement than the placebo group. Przybyla et al used a nonparametric test to lessen the effects of outliers. To be more conservative here, the calculations here dropped the most extreme high and low data values before estimating effect sizes. With that approach, the 29% increase corresponds to an effect size of 0.8 SD units (mean/SD = 0.128/0.159). Similar results were found using CRP data from Pilot Finding 1. The effect size for change in CRP is 0.85 SD units (mean/SD = 0.665/0.780 for log-transformed data). Having at least 20 subjects per group will provide 80% or greater power to detect a mean shift of 0.8-0.85 SD units at a significance level of 5% for the following Aim 1 hypotheses:

- a. The response to vaccination will be greater in the supplement than the placebo group. The change between times K and A (Table 6) will be compared between groups.

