- f. The proliferative capacity of peripheral blood mononuclear cells will be greater in the supplement than the placebo group. The change between times G and C will be compared between groups. The change between times I and E will also be compared between groups.
- g. The resting number of muscle CD163+ macrophages will increase in the supplement but not in the placebo group. The change between times H and D will be compared between groups.
- h. The number of muscle CD163+ macrophages will increase after acute exercise in the supplement but not in the placebo group. The change between times J and H will be compared to change between times F and D for both groups.
- i. Resting NFkB activity will decrease and PI3K activity will increase in the supplement group but not in the placebo group. The change between time points H and D will be compared between groups.
- j. In response to acute exercise, NFkB activity will be lower and PI3K activity will be greater in the supplement group than in the placebo group. The change between times J and H will be compared to change between times F and D for both groups. *Responses similar to NFkB are predicted for FOXO1, and responses similar to PI3K are expected for STAT3, AKT, P38 MAPK, and ERK 1 and 2.*

Aim 2 Power: Aim 2 will determine whether supplement consumption increases muscle adaptation to 12-weeks of resistance training. The representative response measure for this objective is post-training percent increase in muscle strength. In a similar study, Trappe et al sought to improve strength gain by resistance training plus drug treatment. The drug treatment group gained significantly more strength by 25.1% than the group receiving placebo (26.4% vs. 21.1%, $P<0.05$) [23]. The previous findings presented here (Finding 4) indicate that older subjects completing a 12-week training program but not taking supplements will experience an average strength gain of $25 \pm 8\%$. If treatment with the proposed supplement improves strength similarly to the Trappe drug treatment, subjects in the supplement group will improve strength by an average of 31% (i.e., 25.1% greater than those of the placebo group). This translates to an approximate effect size of 0.8 SD units ($0.25*0.251/0.08$) if variances are pooled for the groups compared. With 20 subjects per group, there will be 80% power to detect a mean shift of 0.8 SD units using a significance level of 5% for the Aim 2 hypotheses:

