- a. The amount of strength gained from 12-weeks of training will be greater in the supplement than the placebo group. The change between times L and B will be compared between groups.
- b. The amount of muscle size gained from 12-weeks of training will be greater in the supplement than the placebo group. The change between times L and B will be compared between groups.
- c. The increase in muscle function after 12-weeks of training will be greater in the supplement than the placebo group. The change between times L and B will be compared between groups.
- d. The increase in muscle satellite cells after 12-weeks of training will be greater in the supplement than the placebo group. The change between times M and D will be compared between groups.
- e. The increase in muscle myonuclei after 12-weeks of training will be greater in the supplement than the placebo group. The change between times M and D will be compared between groups.
- f. The increase in muscle fiber size after 12-weeks of training will be greater in the supplement group than the placebo group. The change between times M and D will be compared between groups.

Aim 3 Power: Aim 3 will determine if supplement consumption increases the retention of exercise-derived benefits post-training during 26 weeks of long-term follow-up. The representative response measure for this objective is the strength gain retained during long-term follow-up after exercise training is completed. Lemmer et al observed an average gain in muscle strength of 27% ($P<0.01$) in older men after strength training which is similar the 25% gain presented here in Finding 4 [65]. However, at

31-weeks of post-training follow-up, strength had decreased to be about 9% above pre-training levels. Assuming the same level of variation among our subjects in retention of strength gain as the observed 8% SD for strength gain in Finding 4, then a 0.8 SD effect size would be about 6.4% ($0.8*0.08$), translating to our supplement group retaining strength of 12.4% above pre-training levels. With 20 subjects per group, there will be 80% power to detect a mean shift of 0.8 SD units using a significance level of 5%. If the SD for retention of strength is smaller than 8%, then we will have higher power to detect the same difference or equal power to detect smaller differences for the following Aim 3 hypotheses:

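### The 8% SD used to power Aims 2 and 3 cannot come from the pilot data the protocol reports; power for the planned strength difference is about 22–31%, not 80%

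*Combined protocol and SAP*

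**What the plan says.** Preliminary Studies, Finding 4, describes the pilot: "Older (61-78 yrs) men (N=3) and women (N=5) completed 12-weeks" of resistance training. It gives the spread of the results: "Muscle size change range from -1% to +18% while strength increase ranged from +8% to +65" (percent).

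Statistical Plan, Aim 2 Power, attributes a mean strength gain of 25 ± 8% to Finding 4. It applies a 25.1% relative improvement taken from a cited drug-plus-training trial, so that "subjects in the supplement group will improve strength by an average of 31" percent. It then divides 0.25 × 0.251 by 0.08: "This translates to an approximate effect size of 0.8 SD units".

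Aim 3 Power carries the same figure over to strength retained after detraining, calling it "retention of strength gain as the observed 8% SD for strength gain in Finding 4", and derives a difference of 6.4 points (0.8 × 8).

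Both aims conclude: "With 20 subjects per group, there will be 80% power to detect a mean shift of 0.8 SD units". The opening of the Statistical Plan fixes the test ("Power calculations were based on using a one-sided t-test to compare independent groups") and the error rate ("at a 5% level of significance").

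**The concern.** The protocol uses the 8 as a standard deviation in both aims. The range it reports for the same pilot is 57 points wide in eight people, and the largest gain lies 40 points above the stated mean. Those figures do not fit an SD of 8.

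Strength is the representative measure on which both aims are sized, and the data and safety monitoring section says these power calculations justify the sample size. If the SD is two to three times larger, the trial has little chance of showing the strength benefit it was planned to find. A null result set beside a stated 80% power would then be taken as evidence against the supplement when it would be close to uninformative.

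**Working it through.** **Inputs.** n = 20 per group; one-sided 5% two-sample t-test (Statistical Plan). Aim 2 difference = 25 × 0.251 = 6.275 points. Aim 3 difference = 6.4 points. Finding 4: n = 8, minimum 8, maximum 65. Mean 25 (Aim 2 Power).

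**Power formula.** With d = difference/SD, noncentrality λ = d√(20/2) and 38 degrees of freedom, power = P(T > t₀.₉₅,₃₈), where T is noncentral t with parameter λ.

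**Step 1: the plan's own figure.** d = 0.8 gives 79.9%. The unrounded Aim 2 value, 6.275/8 = 0.784, gives 78.6%. The stated 80% therefore follows from its inputs, and the question is the SD.

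**Step 2: smallest SD the pilot range allows.**
- Whatever the mean: put the other six values at the midpoint of 8 and 65. Sum of squares = 2 × 28.5² = 1624.5; SD = √(1624.5/7) = 57/√14 = 15.2.
- With mean 25: the other six sum to 200 − 73 = 127, so the minimum has each at 21.17. Sum of squares = 17² + 40² + 6 × 3.83² = 289 + 1600 + 88 = 1977; SD = √(1977/7) = 16.8.
- In reverse: eight values with SD 8 can span at most 8√14 = 29.9 points, and none can lie more than 8 × 7/√8 = 19.8 from the mean. The reported figures are 57 and 40.

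**Step 3: largest SD with mean 25.** Two values at 65, five at 8 and one at 30. Sum of squares = 3200 + 1445 + 25 = 4670; SD = √(4670/7) = 25.8.

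**Step 4: standard-error reading.** SD = 8 × √8 = 22.6, inside the interval 16.8 to 25.8. The CT section gives the size gain from the same study as 7.4 ± 2.0%, and Finding 4 gives its range as −1% to +18%. That range needs an SD of at least 19/√14 = 5.1, so the 2.0 cannot be an SD either. As a standard error it implies SD = 2.0√8 = 5.7, which fits.

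**Step 5: power recomputed, 20 per group.**

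| SD | Basis | Aim 2 d | Aim 2 power | Aim 3 d | Aim 3 power |
|---|---|---|---|---|---|
| 8 | as stated | 0.784 | 79% | 0.800 | 80% |
| 15.2 | minimum, any mean | 0.412 | 36% | 0.420 | 37% |
| 16.8 | minimum, mean 25 | 0.373 | 31% | 0.381 | 32% |
| 22.6 | ±8 is a standard error | 0.277 | 22% | 0.283 | 22% |
| 25.8 | maximum, mean 25 | 0.243 | 19% | 0.248 | 19% |

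**Step 6: what 20 per group can detect.** 80% power needs d ≈ 0.80, that is 0.80 × 16.8 = 13.4 points to 0.80 × 22.6 = 18.1 points. By the normal approximation, 80% power for 6.275 points would need about 89 (SD 16.8) to 161 (SD 22.6) evaluable subjects per group. With no dropout, 25 per group gives 37% and 25% for Aim 2.

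**The case against.** **Trimming.** The Statistical Plan drops the most extreme high and low values before estimating effect sizes. Had 8 and 65 been removed here too, six values with mean 25 and SD near 8 are possible: 15, 18, 22, 25, 33, 37 has SD 8.6. But trimming is described only for Aim 1. An SD from trimmed data would also not describe the untrimmed participants the trial compares; restoring 8 and 65 to that set raises its SD to 17.7. If instead 25 is the mean of all eight, dropping only the 65 leaves seven averaging (200 − 65)/7 = 19.3, so the 25% no longer applies.

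**A different measure.** Finding 4 does not itself print 25 ± 8%, and its figure concerns knee extension, while the programme tests three lifts. The two figures might describe different summaries. The protocol does not say so and attributes both to Finding 4.

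**Uncertainty and test choice.** An SD from eight subjects is imprecise: the normal-theory 95% interval around 16.8 is about 11.1 to 34.2, and at 11.1 Aim 2 power would be 54%. The plan allows non-parametric tests when there are outliers, and with some assumed skewed shapes a rank test does clearly better than the t-test. Both points stand as limits on how exactly true power is known. Neither restores 8 as an observed SD, and the stated 80% is itself a t-test figure based on that SD.

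**The standard-error reading is inferred.** With n = 8, the CT result read as a standard error gives t = 3.7 and two-sided P of about 0.008, not the stated 0.002. Read as an SD, P would be about 0.00002, much further away. The 22% end depends on this reading; the 31% end does not.

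**Aim 3.** The documents report no SD for retention, so its 22–32% is conditional on the carry-over that the plan itself makes.

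**Generic statement.** Twenty per group does give 80% power for 0.8 SD. What fails is translating 0.8 SD into 6.3 or 6.4 points of strength.

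**Conclusion.** The concern holds. An observed SD of 8 is arithmetically incompatible with eight gains that include 8% and 65%. Under the plan's own t-test, one-sided 5% level and 20 per group, power for the Aim 2 strength difference is at most 31% with a pilot mean of 25, and 22% if the ±8 is a standard error. Aim 3 gives 32% and 22% if the gain SD carries over to retention. The lowest value the pilot figures allow is about 19%.

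This assumes that the range and the 25 ± 8% describe the same eight untrimmed subjects and the same strength measure, as the protocol presents them, and that the pilot SD is used as the planning SD, as the plan does. The power statement for strength is wrong as written and must be corrected.

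**What to change.** Recompute the between-subject SD of strength gain from the eight individual Finding 4 values. State which strength measure it refers to, and whether the ±8 was an SD, a standard error or a trimmed figure. Use the recomputed SD in Aim 2 Power, and in Aim 3 Power as an explicit assumption.

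Then restate both aims in one of two ways: power of about 22–31% (Aim 2) and 22–32% (Aim 3) for differences of 6.3 and 6.4 points, or a difference of about 13 to 18 points detectable with 80% power. Replace these ranges with exact figures once the SD is known. Delete the statement that 31% versus 25% corresponds to 0.8 SD.

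The cost is re-wording of the power section and a less favourable stated power. No extra participants or procedures are needed.

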- b. Use of Certain Medications: it is unknown how certain medications (specifically those used to control inflammation) and other age-associated medical issues will influence the variables of interest to the study. Due to this possibility, medications and medical problems will be recorded and used as potential confounding variables in the statistical or exploratory analyses.

15. Computed Tomography Scan of the Thigh

- a. **Procedure:** Muscle Cross-Sectional Area and composition will be determined by the hospital imaging service using computed tomography (CT) scan of the mid-thigh at pre-training, post-training, and at the end of the study. The service performed CT scans for our previous study which showed that size increased ($P=0.002$, $7.4 \pm 2.0\%$) in older adults after 12-weeks of

training [3]. Subjects are carefully positioned in the scanner and boney land marks are used to ensure precise mid-thigh location for each scan. Analysis of scans will be completed using a program such as Slice-O-matic (Montreal, Canada) to discern between bone, fat, and muscle.

CT scan data is transferred from the Imaging service to the study on a CD which is not encrypted per se. However, the risk of an unintended recipient accessing the data is particularly low because specialized software is required to view the data. Furthermore, the data is a cross-sectional image of the thigh which looks like a slice of ham (i.e. not sensitive). The information will be labeled with the subject study ID, not name or SSN. Transport of the disk from the LR to NLR VA will occur in a locked bag and the disks will be maintained according to CAVHS regulations.

- b. **Benefit:** The CT scan of the thigh is of no direct benefit to the subject though the measure provides important scientific knowledge of the effects of exercise training, detraining, and nutritional supplementation in older adults.
- c. **Risk:** The procedure will expose subjects to radiation. The total amount of radiation the subjects will be exposed to per scan (6 mSv) is approximately the same as the average exposure an individual has from natural sources per year. Having three scans in one year creates a very small increase (from 44.9% to 44.95%) in the risk of cancer for the average 70 year old male (www.xrayrisk.com).

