- b. The resting ratio of CD4+ to CD8+ t-cells will increase in the supplement but not in the placebo group. The change between times G and C will be compared between groups.
- c. The change in t-cell subsets after acute exercise will be greater in the supplement than the placebo group. The change between times I and G will be compared to the change between times E and C for both groups.
- d. Resting cytokine levels will decrease in the supplement but not in the placebo group. Change will be compared between groups for blood (times G and C) and muscle (times H and D). *Similar results are predicted for the MuRF and MAFbx atrophy-related transcripts.*
- e. The increase in cytokine levels after acute exercise will be greater in the placebo group than the supplement group. For both groups, change between times I and G will be compared to the change

Table 6. Time points are lettered for clear reference by the stated hypotheses.	
BASELINE MEASURES (WEEKS 1-5)	
A.	Blood draw at study enrollment for measuring pre-vaccination antibody titers
B.	Assessment of muscle strength, mass, and function at baseline
C.	Blood drawn prior to acute exercise at baseline
D.	Muscle biopsy prior to acute exercise at baseline
E.	Blood drawn 1 hr after acute exercise at baseline
F.	Muscle biopsy 72 hrs after acute exercise at baseline
POST-SUPPLEMENT RUN-IN MEASURES (WEEK 8)	
G.	Blood drawn prior to acute exercise after 2-weeks of supplementation
H.	Muscle biopsy prior to acute exercise after 2-weeks of supplementation
I.	Blood drawn 1 hr after acute exercise after 2-weeks of supplementation
J.	Muscle biopsy 72 hrs after acute exercise after 2-weeks of supplementation
MEASURES DURING TRAINING PERIOD (WEEKS 9-20)	
K.	Blood draws at weeks 1 and 2 post-vaccination for measuring antibody response
POST-TRAINING MEASURES (WEEK 21)	
L.	Assessment of muscle strength, mass, and function after completion of training
M.	Muscle biopsy 72 hrs after final exercise bout of training
MEASURES DURING POST-TRAINING FOLLOW-UP (WEEKS 22-4)	
N.	Assessments of strength, mass, and function after 16 and 26 weeks of detraining

between E and C for blood, and for muscle the change between times J and H will be compared to the change between times F and D.

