- a. The change in strength during the detraining period will be smaller in the supplement than the placebo group. The change between times N and L will be compared between groups.
- b. The change in muscle size during the detraining period will be smaller in the supplement than the placebo group. The change between times N and L will be compared between groups.
- c. The change in muscle function will be smaller in the supplement than the placebo group. The change between times N and L will be compared between groups.

Reference List

4. Ellis A. Dietary Supplements and Aging Muscle. University of Alabama at Birmingham and the National Center for Complementary and Alternative Medicine (NCCAM) [2012 Available from: URL:<http://www.clinicaltrials.gov/ct2/results?term=NCT01057082>

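### Aim 3's worked power example prints 12.4% where its own inputs give 15.4%, and it is built on strength above pre-training while the Aim 3 tests compare the loss from post-training (N minus L)

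*Combined protocol and SAP*

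**What the plan says.** All of this is in the Statistical Plan of the combined protocol and SAP.

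- **Reference.** Aim 3 Power cites a study of older men whose strength rose 27% with training. At 31 weeks of follow-up, "strength had decreased to be about 9% above pre-training levels".
- **SD.** The SD is borrowed from the training gain in Finding 4: "Assuming the same level of variation among our subjects in retention of strength gain as the observed 8% SD for strength gain".
- **Effect.** From that SD, "then a 0.8 SD effect size would be about 6.4" percent, shown as 0.8*0.08.
- **Result.** The paragraph ends the example with "translating to our supplement group retaining strength of 12.4% above pre-training levels". It then claims 80% power with 20 per group for a 0.8 SD shift at the 5% level, for the Aim 3 hypotheses that follow.
- **Test.** Hypothesis a reads "The change in strength during the detraining period will be smaller in the supplement than the placebo group", and for each of the three hypotheses "The change between times N and L will be compared between groups". In Table 6, L is the post-training assessment, N the follow-up assessment and B the baseline.
- **Aim 2.** Aim 2 Power assumes a strength gain at L of 25% (SD 8%) without the supplement and 31% with it, the latter being 25.1% greater in relative terms.

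**The concern.** Two things do not fit. First, the printed end point of the example does not follow from its own reference and effect. Second, the example measures how far strength at N lies above pre-training (N against B), but the planned test measures how much strength is lost after training stops (N minus L). An advantage of 6.4 points at N says nothing about loss until the difference at L is known, and elsewhere the plan assumes that the supplement group is already ahead at L.

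Retention is one of three specific aims, and the Data Safety and Monitoring Plan rests the sample size on the protocol's power calculations. If the example does not illustrate the planned test, the plan has not shown what difference in loss, in percentage points, Aim 3 could detect.

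**Working it through.** **1. Stated power.** Inputs from the Statistical Plan: one-sided independent-groups t-test, 5% level, 20 per group, shift of 0.8 SD. The noncentral t with 38 degrees of freedom gives 79.9%, so the stated 80% is reproduced. It applies to any two-group contrast whose true difference is 0.8 of that contrast's own SD.

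**2. The worked example.** 0.8 × 8 = 6.4 points, reproduced. Reference plus effect is 9 + 6.4 = 15.4, not 12.4. Other routes from figures in the plan also fail:

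- keeping the cited fraction of a 25% gain: 25 × 9/27 + 6.4 = 14.7
- subtracting the cited 18-point loss from 25: 25 − 18 + 6.4 = 13.4
- applying Aim 2's relative improvement to 9: 9 × 1.251 = 11.3
- scaling 9 from 31 to 26 weeks: 9 × 26/31 + 6.4 = 13.9

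A result of 12.4 needs a reference of 12.4 − 6.4 = 6.0%, which Aim 3 Power does not give.

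**3. Moving from N against B to N minus L.** With S for supplement and P for placebo,

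(N_S − L_S) − (N_P − L_P) = (N_S − N_P) − (L_S − L_P).

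The 6.4-point difference at N equals the difference in loss only if L_S − L_P = 0. The SD must also be that of N minus L. If the SD is 8 at each time with correlation r, then SD(N − L) = 8 × √(2(1 − r)), which equals 8 only at r = 0.5. The documents give no r, so a range is shown in step 5.

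**4. Using the plan's own Aim 2 values at L.** Placebo is 25. Supplement is 31 as printed, or 25 × 1.251 = 31.275 unrounded.

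- Placebo change: 9 − 25 = −16.0.
- Supplement change with 15.4 at N: 15.4 − 31 = −15.6, or 15.4 − 31.275 = −15.875.
- Difference in loss: 0.4 or 0.125 points.
- Supplement change with the printed 12.4 at N: 12.4 − 31 = −18.6, or 12.4 − 31.275 = −18.875. The supplement group would then lose 2.6 to 2.9 points more than placebo, opposite to hypothesis a.

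The near-cancellation is no accident. Aim 2's difference at L (6 to 6.3 points) and Aim 3's difference at N (6.4 points) are both about 0.8 of the same 8% SD.

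**5. Power on N minus L** (20 per group, one-sided 5%; SD 8 at each time and r are assumptions):

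| r | SD of N − L | 6.4 points (arms equal at L) | 0.4 points (Aim 2, 31%) | 0.125 points (Aim 2, 31.275%) |
|---|---|---|---|---|
| 0 | 11.31 | 54.5% | 6.2% | 5.4% |
| 0.25 | 9.80 | 64.9% | 6.5% | 5.4% |
| 0.5 | 8.00 | 79.9% | 6.8% | 5.5% |
| 0.75 | 5.66 | 96.9% | 7.7% | 5.7% |
| 0.9 | 3.58 | nearly 100% | 9.7% | 6.2% |

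**The case against.** The strongest reply is that the slip sits in an illustration. The paragraph gives the effect with its formula and ties the 80% to 0.8 SD and 20 per group. Whether the 9% or the 12.4% is wrong, the intended difference is still 6.4 points, so the power claim is untouched. That stands. A reader might infer from 12.4 − 9 = 3.4 that the trial really targets 3.4 points and is badly underpowered for it. The documents do not support this: it would require both the explicit 6.4% and the explicit 0.8 SD to be wrong.

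A second reply is that the plan does supply an SD: it assumes 8% for retention of strength gain, applies the calculation to the Aim 3 hypotheses, and says that a smaller SD would give more power. Read generously, that 8% could be the SD of N minus L. It would therefore be too strong to say that no difference or SD is given. Even on that reading, however, the 6.4 points still need equal arms at L. The paragraph does not state this, and Aim 2 assumes otherwise.

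A third reply is that the aims were designed to be independent, so Aim 3 may be powered as though Aim 2 had no effect. That is a coherent choice, but the plan would have to say so, because Aim 3 measures loss from the level that Aim 2 is meant to raise.

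**Conclusion.** The point holds as a correction to the sample-size justification. The printed 12.4% is inconsistent with the 9% and 6.4% beside it, and which figure is the slip cannot be settled from the documents. The 80% for a standardised 0.8 SD shift is right.

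What lacks support is the translation into points for the tested contrast. Under the plan's own Aim 2 and Aim 3 examples taken together, the N minus L difference is about 0.1 to 0.4 points and power is about 5% to 10%. That rests on 15.4% at N, an SD of 8 at each time and an assumed correlation of 0 to 0.9. The reference levels come from a cited study at 31 weeks, not 26.

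A reader might infer that the N minus L test is faulty or that Aim 3 as a whole has power near 5%. Neither follows. In that scenario there is almost no difference in loss to detect, so a null result would be correct. The scenario shows that the two worked examples cannot both illustrate their planned tests, not that N minus L is the wrong contrast. The 8% SD is taken here as the plan gives it; whether Finding 4 supports it is a separate question.

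**What to change.** 1. Reconcile the 9%, 6.4% and 12.4% in Aim 3 Power, stating which input or result was intended.
2. Keep N minus L as the Aim 3 test and restate the power example on that scale. Give the assumed difference in loss, the SD of N minus L with its source, and the assumed difference between arms at L. Make the last agree with Aim 2, or say explicitly that Aim 3 is powered assuming equal arms at L.
3. If no source for those quantities is available, state the 80% only as power for a standardised 0.8 SD difference and withdraw the translation into 6.4% and 12.4%.

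The change is to wording only: no new data, no change to the number of participants and no change to the planned tests. The cost is that the detectable difference or the power stated for Aim 3 may become less favourable once it is expressed on the tested scale.
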